7.0 DEMOGRAPHICS AND BASELINE CHARACTERISTICS

Demographics and baseline characteristics will be summarized for the ITT Population. Descriptive statistics will be presented for the continuous variables of age, height, weight, BMI, IRLS total score at baseline, and the duration of RLS symptoms. Frequencies and percentages will be presented for the categorical variables of sex (at birth), ethnicity, race, category of medication that the subject is refractory to, and categories of medication that the subject is currently taking.

8.0 EFFICACY AND SAFETY ANALYSES

8.1 Primary Efficacy Endpoint Analysis

The primary efficacy endpoint is the response on the Clinical Global Impressions-Improvement (CGI-I) scale at Week 24 of Arm 1 relative to Baseline (RESTFUL study entry) where a "successful" response is defined as a response of "Much Improved" or "Very Much Improved". This endpoint will be summarized by treatment group using frequencies and percentages.

The 95% confidence interval will be presented for the proportion of "successful" responses. If there are any missing data for this endpoint, last observation carried forward (LOCF) methods will be used to impute the missing data.

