16.16. Subject Discontinuation

A subject may be removed from the study prior to completion for any of the following reasons:

- Voluntary withdrawal of consent
- Adverse event preventing further study participation
- Investigator believes risk of further subject participation outweighs benefit
- Persistent non-compliance or lost to follow-up
- Pregnancy
- Subject no longer meets inclusion criteria
- [For arms 1 and 3 only] Subject makes a significant change to dosage of medications known to interfere with sleep or RLS symptoms, including sleep medications, antidepressants, sedative antihistamines.

Investigational Plan, Protocol CT-05 (Extension Study)

Document #: CT-4

Rev: 1.0

Effective: 11/24/2021

• [For arms 1 and 3 only] Insufficient device availability (see 16.16.1 below)

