5.3 Handling of Dropouts and Missing Data

If there are any missing data for efficacy endpoints, the "Last Observation Carried Forward" imputation method will be used to impute the missing data. If no data are available in this study, then the last observation from CT-04 will be carried forward.

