6.0 ANALYSIS POPULATIONS

6.1 Intent-to-Treat (ITT) Population

The Intent-to-Treat (ITT) Population will include all eligible subjects who pass screening and are enrolled into the study. The ITT Population Set will be used for the primary analysis of all efficacy endpoints.

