6.2 Stable Medication Population

The Stable Medication (SM) Population will include all eligible subjects who pass screening, are enrolled into the study, and do not report any of the following changes to prescription RLS medication between completion of the RESTFUL Study and Week 24 of CT-05:

- 1. New prescription RLS medication.
- 2. Change in dose of prescription RLS medication.
- 3. New prescription sleep medication.
- 4. Change in dose of prescription sleep medication.

The Stable Medication Population will be used for a secondary analysis of key secondary efficacy endpoints #6-11. This is intended to account for the differences in instructions regarding changes to prescription medications for Arms 1 and 2.

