6.3 Per Protocol Population

The Per Protocol (PP) population will include all subjects in Arms 1 and 2 who pass screening, undergo the assigned treatment, and have complete and evaluable Week 24 data, except that:

Subjects will be excluded from the Per Protocol Population if one or more of the following occurs:

- 1. Discontinuation from the study.
- 2. Incomplete or missing data for the endpoint.
- 3. [Arm 1 only] Change to RLS medication during the study that is deemed clinically significant by the investigator.
- 4. [Arm 1 only] Zero total device uses during the study.
- 5. Other protocol deviation occurs that is deemed clinically significant by the investigator.

The PP Population will be used for a secondary analysis of all efficacy endpoints.

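### In Arm 1, added or increased RLS or sleep medication before Week 24 is never itself treated as non-response, so the single-arm responder rates can credit a drug effect to the device

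*SAP*

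**What the plan says.** The primary endpoint (SAP 8.1) is the Week 24 CGI-I in Arm 1 relative to RESTFUL entry, where a successful "response is defined as a response of 'Much Improved' or 'Very Much Improved". It is estimated, not tested: "The 95% confidence interval will be presented for the proportion of 'successful' responses". For missing values, "last observation carried forward (LOCF) methods will be used to impute the missing data", and SAP 5.3 adds: "If no data are available in this study, then the last observation from CT-04 will be carried forward". SAP 8.2 treats key secondary #1 in the same manner.

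The primary analysis set is ITT (SAP 6.1): "The Intent-to-Treat (ITT) Population will include all eligible subjects who pass screening and are enrolled into the study".

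Four provisions deal with medication changes in Arm 1:

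- **Instruction.** Subjects are told to keep RLS medication constant (SAP 3.1, 3.2). Protocol 16.10 extends this to other drugs that affect RLS symptoms, including sleep medication.
- **Removal.** Protocol 16.16 lists reasons for which a subject may, not must, be removed. One is: "Subject makes a significant change to dosage of medications known to interfere with sleep or RLS symptoms".
- **Per Protocol exclusion.** SAP 6.3 excludes an Arm 1 subject for a "Change to RLS medication during the study that is deemed clinically significant by the investigator". PP is a secondary analysis.
- **Stable Medication (SM) set.** SAP 6.2 excludes subjects with a new or dose-changed prescription RLS or sleep drug between RESTFUL completion and Week 24. Its scope is limited: "The Stable Medication Population will be used for a secondary analysis of key secondary efficacy endpoints #6-11".

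**The concern.** A subject who needs more RLS or sleep medication while using the device has had an event that bears directly on the outcome. The CGI-I compares the past week's symptoms with baseline (Protocol 16.14). It does not separate what the device did from what a new drug did. In a single-arm proportion no comparison group offsets a drug effect, so such a response cannot be attributed to the device.

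The study objective is longer-duration efficacy of the device, and the Week 24 responder rate will be read as durable device response. The SAP already recognises the problem for the comparison of Arm 1 with Arm 2, and created the SM set for it. It gives the uncontrolled endpoints no equivalent. Endpoints #2 to #5 are also exposed, for example a new sleep drug and the MOS sleep indices.

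**Working it through.** **No figure to reproduce.** SAP 3.4 says no sample size was determined. Neither document gives an expected responder rate, an expected rate of medication change, or a number for Arm 1.

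**How a changer is classified for the primary endpoint:**

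| Situation | ITT (primary) | PP (secondary) |
|---|---|---|
| Stays in, Week 24 CGI-I of 1 or 2 | Success | Excluded if the investigator judges the change significant; otherwise success |
| Stays in, Week 24 CGI-I of 3 to 7 | Failure | Excluded on the same judgement; otherwise failure |
| Removed, last CGI-I of 1 or 2 | Success by LOCF | Excluded (discontinued) |
| Removed, last CGI-I of 3 to 7 | Failure by LOCF | Excluded (discontinued) |

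In no cell is the change itself a non-response.

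**What LOCF carries.** During device use CGI-I is scheduled only at Weeks 8, 16 and 24 (Protocol Table 4, SAP Table 1). Suppose a subject responds at Week 8, loses benefit, starts a drug and is removed in Week 13. The Week 8 success becomes the Week 24 value. Had removal come after Week 16, a failing Week 16 score could have been carried instead. PGI-I is collected more often, so its carried value is usually more recent, but the rule is the same.

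**Size of the gap.** Let N be the number in Arm 1, f the share with a new or increased drug before Week 24, q the share of those counted as responders, and R the responders among the rest.

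- As-observed ITT rate = (R + N·f·q) / N
- Changers counted as non-responders = R / N
- Difference = f × q

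Difference in percentage points, with f and q assumed:

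| f | q = 0 | q = 50% | q = 100% |
|---|---|---|---|
| 5% | 0 | 2.5 | 5 |
| 10% | 0 | 5 | 10 |
| 20% | 0 | 10 | 20 |

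**Worked example, all inputs assumed.** Take N = 80, 8 changers (f = 10%), 6 of them scored as responders (q = 75%), and 43 responders among the other 72. Intervals are exact (Clopper-Pearson).

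- As observed: (43 + 6)/80 = 49/80 = 61.3% (95% CI 49.7 to 71.9)
- Changers as non-responders: 43/80 = 53.8% (42.2 to 65.0)
- All changers excluded: 43/72 = 59.7%

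The difference between the first two is 6/80 = 7.5 points, which equals 10% × 75%. Excluding changers gives a rate below the as-observed one here, but still above the rate that counts them as failures. An exclusion analysis therefore does not replace the second figure.

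**The case against.** A reader might infer that changers count as successes or are dropped, and never count as failures. The documents do not support that. ITT drops nobody for a medication change, and a changer rated 3 to 7, observed or carried forward, is a failure. Nor does every route raise the rate: exclusion lowers it in the example above. It is only against a rule that fails all changers that the planned rates cannot be lower.

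Three other points carry weight.

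- **Sleep drugs and PP.** The medication item in SAP 6.3 names only RLS medication, but a sleep-drug change can still lead to exclusion through discontinuation or as another clinically significant deviation, because Protocol 16.10 asks for stable sleep medication.
- **The SM analysis already covers much of this.** Endpoint #6 uses the same CGI-I variable as the primary endpoint, and #7 to #11 mirror #1 to #5. SAP 8.2 summarises the CGI-I rate by Arm, so the Arm 1 column of Table 2.7 should show a stable-medication responder rate. What remains missing is its use for the primary endpoint with an interval for Arm 1 alone. SAP 3.5 promises intervals for the key secondary endpoints, but #6 to #11 are between-arm comparisons, so the text does not commit to a single-arm interval. The SM set also excludes changers and does not fail them.
- **As-observed scoring in ITT is a legitimate choice** for an open-label extension that estimates and does not test. Counting every changer as a failure would also fail subjects whose sleep-drug change had nothing to do with lost device benefit. This argues against making non-response the sole primary rule, but not against reporting it.

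The other safeguards (the instruction, optional removal, counts of RLS-drug changes in Table 2.18, by-subject listings) limit or describe the problem. None links a change to response in a planned analysis.

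**Conclusion.** The gap is real but narrower than it first looks. For the primary endpoint and #1 the SAP states no handling for an added or increased RLS or sleep drug, and no planned analysis counts it as non-response. PP removes only some changers, partly on the judgement of an open-label investigator. The fixed-rule SM set is not assigned to these endpoints. The single-arm rates can therefore include improvement due to medication, or a success that predates removal for a medication change.

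The size cannot be found from the documents. It is f × q: zero if no changer is counted as a responder, and 2.5 to 20 points for assumed f of 5 to 20% and q of 50 to 100%. The documents do not show that inflation will occur, only that the plan would not reveal how much of the rate depends on it. This should be fixed, but it does not invalidate the as-observed rate.

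**What to change.** - **SAP 8.1, and key secondary #1 in SAP 8.2.** State that the ITT rate scores subjects regardless of medication change. Beside it, prespecify and report a responder rate with 95% CI in which an Arm 1 subject counts as a non-responder if a new or increased prescription RLS or sleep drug is recorded between RESTFUL completion and the Week 24 rating. Use the drug categories of SAP 6.2, and let this rule override LOCF.
- **SAP 6.2.** Also report single-arm SM results for Arm 1, with 95% CI, for the primary endpoint and #1 to #5.
- **Scope.** Confine the non-responder rule to the single-arm responder endpoints, because Arm 2 is permitted to change medication.

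The cost is SAP wording and a few extra table columns. Concomitant medication is already collected at Day 0 and at Evals 2 to 8. The downside is a possibly less favourable rate. No change to the medication instructions or the removal rules is proposed.

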8.2 Key Secondary Efficacy Endpoints Analyses

Key secondary endpoint #1 will be treated in the same manner as the primary efficacy endpoint; the 95% confidence interval will be presented for the proportion of "successful" responses.

The remaining key secondary efficacy endpoints below will be analyzed using a fixed sequential method in the order they are listed. Subsequent secondary efficacy endpoints will only be analyzed

if all prior secondary efficacy endpoint analyses resulted in rejection of the null hypothesis (e.g., secondary efficacy endpoint #4 would only be tested if the primary analyses of the secondary efficacy endpoints #2 and #3 both result in rejection of the null hypothesis). Analyses of subsequent secondary endpoints will continue hierarchically until the first analysis that results in failure to reject the null hypothesis, and some or all of the secondary efficacy endpoint analyses may not be formally performed.

The key secondary efficacy endpoints are as follows:

Comparisons between Arm 1 Week 24 and baseline (entry to the RESTFUL Study):

- 1. PGI-I responder rate (defined as for CGI-I) at Week 24 of Arm 1 relative to entry to the RESTFUL Study.
- 2. Mean reduction in IRLS total score at Week 24 of Arm 1 relative to entry to the RESTFUL Study.
- 3. Mean reduction in MOS-II score at Week 24 of Arm 1 relative to entry to the RESTFUL Study.
- 4. Mean reduction in MOS-I score at Week 24 of Arm 1 relative to entry to the RESTFUL Study.
- 5. Frequency of RLS symptoms (based on IRLS question #7) at Week 24 of Arm 1 relative to entry to the RESTFUL Study.

Comparisons between Arm 1 Week 24 and Arm 2 Week 24:

- 6. CGI-I responder rate (defined as for CGI-I) at Week 24 of Arm 1 compared to Week 24 of Arm 2.
- 7. PGI-I responder rate (defined as for CGI-I) at Week 24 of Arm 1 compared to Week 24 of Arm 2.
- 8. Mean reduction in IRLS score at Week 24 of Arm 1 compared to Week 24 of Arm 2.
- 9. Mean reduction in MOS-II score at Week 24 of Arm 1 compared to Week 24 of Arm 2.
- 10. Mean reduction in MOS-I score at Week 24 of Arm 1 compared to Week 24 of Arm 2.
- 11. Frequency of RLS symptoms (based on IRLS question #7) at Week 24 of Arm 1 compared to Week 24 of Arm 2.

Comparisons between Arm 1 Week 24 and baseline (entry to the RESTFUL Study):

The PGI-I response for Arm 1 Week 24 relative to Baseline (RESTFUL study entry) will be analyzed in the same manner as the primary efficacy endpoint.

8.3 Safety Analyses

The proportion of subjects having one or more adverse events (AEs) between study entry and Week 24 will be presented by Arm. The proportion of subjects reporting AEs between Week 25 and Week 32 will be presented for Arm 1. Similar analyses will be done for serious adverse events (SAEs), device-related SAEs, and device-related AEs

Adverse events will be coded using the Medical Dictionary for Regulatory Activities (MedDRA). AEs will be summarized at the subject level using counts and percentages by MedDRA system organ class (SOC) and preferred term (PT). AEs will also be summarized at the event level using

counts and percentages by SOC/PT and seriousness, by SOC/PT and severity, and by SOC/PT and relationship to the device.

Frequency charts of adverse events occurring at any time during the study will be produced. The proportion of subjects with at least one AE will be presented overall and by SOC. The proportion of subjects with at least one occurrence of individual AEs will be presented for AEs occurring in >3% of subjects overall or within either Arm.

This document, when printed, is valid only until its new revision gets released, or when it becomes obsolete in the eQMS. The user of a printed copy of this document is responsible for using the current revision and for discarding superseded or obsolete revisions. The most current version of this document always resides in the eQMS.

Noctrix Health, Inc. CONFIDENTIAL CL-7 v2.0

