Subjects who have previously completed The RESTFUL Study are consented to one of three Arms, the design of which is illustrated in the flowchart below (Figure 1). Arm 1 is a Direct Roll-Over Extension, Arm 2 is a Control, and Arm 3 is a Delayed Extension. A subject may be asked to participate in Arm 3 after completing Arm 2.

Investigational Plan, Protocol CT-05 (Extension Study)

Document #: CT-4

Rev: 1.0

Effective: 11/24/2021

Arm 1 (Direct Roll-Over Extension) – Arm 1 is only an option for subjects who successfully
complete The RESTFUL Study after enrollment to CT-05 begins at a given clinical site; Arm 1
involves a 24-wk extension period of NTX100 device use followed by an 8-wk period without
device use.

- Arm 2 (Control Group) Arm 2 is an option for subjects who successfully complete the RESTFUL Study before enrollment to CT-05 begins at a given clinical site or subjects who decline to participate in Arm 1. Subjects enrolled in Arm 2 will not receive treatment with the NTX100 device. Arm 2 involves follow-up phone calls to access on RLS progression and medication usage at 8-wks, 16-wks, and 24-wks after the end of The RESTFUL Study. Subjects who are consented more than 8-wks after The RESTFUL Study completion will only complete the remaining follow-ups (e.g. subjects consented 12-wks after The RESTFUL Study will only complete the 16-wk and 24-wk follow-ups).
- Arm 3 (Delayed Extension) Arm 3 is only an option for subjects who successfully complete The RESTFUL Study before enrollment to CT-05 begins at a given clinical site; like Arm 1, Arm 3 involves a 24-wk extension period of NTX100 device use followed by an 8-wk period without device use. Enrollment in Arm 3 of the study begins after a fixed delay upon close-out of the RESTFUL Study; the fixed delay will be >= 24-wks and <= 52-wks, will be the same value for all subjects (+/- 2-wks), and will be determined based on investigational device availability and other constraints. The sponsor will notify each site once Arm 3 is open to enroll study subjects for that site.

•

[figure not shown]
Investigational Plan, Protocol CT-05 (Extension Study)

Document #: CT-4

Rev: 1.0

Effective: 11/24/2021

Figure 1: Study Design Flowchart

5. Blinding

Arms 1 and 3 will be open label. The treatment assignment on each device will be set to Active for all subjects and subjects will be informed that they are received Active treatment.

Arm 2 does not involve treatment.

6. Duration

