16.1. Overview

Arms 1 and 3 involve a 24-week extension of in-home investigational device usage for subjects who previously completed the RESTFUL Study, followed by an 8-week period without investigational device usage to assess the progression of RLS following cessation of treatment. Two separate arms are employed to maximize the number of subjects eligible for any extension phase (Arm 1 and Arm 3) while also maximizing the number of subjects who can proceed directly to the extension phase (Arm 1 only). Notably, in the RESTFUL Study, subjects will have already completed either 4-weeks of device usage (Sham \rightarrow Active) or 8-weeks (Active \rightarrow Active) depending on randomization. Since site staff were blinded to RESTFUL Study treatment assignment, no procedures in this protocol will be affected by RESTFUL Study treatment assignment.

Arm 2 serves as a control arm with matched duration to the 24-week period of investigational device usage; this arm is designed to the assess the changes to medication and RLS symptoms that occur under the conventional standard of care, in the absence of investigational device intervention. Although the duration of Arm 2 states 24-weeks, each subjects participation will vary, since the 24-week period also includes the time between when the subject exits the RESTFUL study and when they enroll in Arm 2 of the CT-05 study. For example, subjects who are consented more than 8-wks after RESTFUL Study completion will only complete the remaining follow-ups (e.g. subjects consented 12-wks after the RESTFUL Study will only complete the 16-wk and 24-wk follow-ups).

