- b. [Cohort 2B] There is a variable delay between RESTFUL Study completion and Arm 2 entry, depending on the time that the subject completed the Restful Study. Subjects will be enrolled either 8-wks, 16-wks, or 24-wks after completion of the RESTFUL Study, +/- 1-wk.

Completion

a. Both Cohorts 2A and 2B are completed 24-wks after completion of the RESTFUL Study
 +/- 1-week. Therefore, the duration of study participation in Arm 2 depends on the delay between RESTFUL Study completion and enrollment in this study.

Baseline

a. For both Cohorts 2A and 2B, baseline refers to RESTFUL Study entry (Eval 1 of Restful Study).

Table 3. Comparison of Study Arms

	Arm 1	Arm 2	Arm 3 Earlier cohort of RESTFUL Study subjects		
Eligibility	Later cohort of RESTFUL Study subjects	RESTFUL Study subjects who don't complete Arm 1			
Start date relative to RESTFUL Study completion	0* days	Less than 24-wks	Fixed delay, >=24-wks and <=52-wks		
End date relative to RESTFUL Study completion	32-wks	24-wks	Variable		
Duration	32-wks	up to 24-wks	32-wks		
Investigational device use	Wks 1-24	None	Wks 1-24		
Baseline	RESTFUL Study entry	RESTFUL Study entry	Entry to this study		

^{*} Up to 2 days if needed

Investigational Plan, Protocol CT-05 (Extension Study)

Document #: CT-4

Rev: 1.0

Effective: 11/24/2021

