Evaluation 1: In-person visit or Phone call for enrollment, including consent, screening, and assessments. For Cohort 2A (see Section 16.2), consent & screening will typically occur in-person on the same visit as Eval 11 for the RESTFUL Study. If the subject's schedule does not permit completion of assessments during this office visit, then these assessments may be conducted via phone follow-up at any time within the 3-days following the office visit.

Evaluation 2: (8-wks after completion of the RESTFUL Study) Phone follow-up to assess RLS symptoms, any changes to daily medications, and adverse events.

Evaluation 3: (16-wks after completion of the RESTFUL Study) Phone follow-up to assess RLS symptoms, any changes to daily medications, and adverse events.

Evaluation 4: (24-wks after Eval #1) Phone follow-up to assess RLS symptoms, any changes to daily medications, and adverse events. Study exit.

Investigational Plan, Protocol CT-05 (Extension Study)

Document #: CT-4

Rev: 1.0

Effective: 11/24/2021

As summarized in Table 5, enrollment to Arm 2 will either occur at either 0-wks (EVAL 1), 8-wks (EVAL 2), 16-wks (EVAL 3), or 24-wks (EVAL 4) after completion of the Restful Study, +/- 6-days. If enrollment occurs at 24-wks, the SF-36 and concomitant medication assessments will only be conducted once.

Table 5. Structure of Arm 2

Delay after RESTFUL study completion	Evals conducted
0-wks	1,2,3,4
8-wks	1,2,3,4
16-wks	1,3,4
24-wks	1,4

TABLE 2: SCHEDULE OF ASSESSMENTS FOR ARM 2

Schedule of assessment	s - Arm 2						
		Eval 1	Eval 2	Eval 3	Eval 4		
		Day 0	Wk-8*	Wk-16*	Wk-24*		
		In-person or					
Assessment	Completed by	Remote	Remote	Remote	Remote		
Screening		Х					
Consent		Х					
Study entry question naire	Staff + subject	X					
ConMeds	Staff	X	х	Х	Х		
AE Monitoring/Reporting	Staff		х	х	х		
IRLS	Staff + subject		х	х	х		
PGFI	Staff + subject		Х	Х	Х		
CGFI	Investigator		х	Х	Х		
MOS-Sleep	Staff + subject		Х	Х	Х		
SF-36	Staff + subject	X			Х		
Study exit questionnaire	Staff + subject				х		
* Duration after Eval 11 of The	RESTF UL Study, not CT-4 enrollm	ent [not all subjects will en	roll in time	to complet	e Wk-8 or \	Wk-16 timepoints	

16.13. Device replacement in Arms 1 and 3

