17.3.2. Safety Analysis

Frequency charts of adverse events occurring at any time during the study will be produced. The proportion of subjects in Arms 1 and 3 reporting one or more adverse events between study entry and Week 24 will be pooled and tabulated. Similar analyses will be done for SAEs and device-related SAEs. Safety analysis will include all subjects who were treated. A Statistical Analysis Plan (SAP) will be developed prior to completion of the first subject in Arm 1 or 3, which may include additional plans for safety analysis.

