3.1 Overview

Subjects who previously completed the RESTFUL Study [Protocol Number: CT-04; ClinicalTrials.gov Identifier: NCT04874155] consent to one of two Arms, the design of which is

illustrated in the flowchart below (Figure 1). Arm 1 is a Direct Roll-Over Extension and Arm 2 is a Control.

- **Arm 1** (Direct Roll-Over Extension) Arm 1 is only an option for subjects who successfully complete RESTFUL Study after enrollment to CT-05 begins at a given clinical site; Arm 1 involves a 24-wk extension period of NTX100 device use followed by an 8-wk period without device use. Subjects in Arm 1 are instructed to maintain constant dose and schedule of RLS medication (if applicable).
- Arm 2 (Control Group) Arm 2 is an option for subjects who successfully complete the RESTFUL Study before enrollment to CT-05 begins at a given clinical site or subjects who decline to participate in Arm 1. Subjects enrolled in Arm 2 will receive no treatment with the NTX100 device during Arm 2. Arm 2 involves assessment during the 24-wks after RESTFUL Study completion. Subjects in Arm 2 are permitted to change RLS medication.

Figure 1: Study Design Flowchart

The schedule of assessments for this study is presented in Table 1.

Table 1: Schedule of Assessments

	Eval 1			Eval 2	Eval 3	Eval 4	Eval 5	Eval 6	Eval 7	Eval 8	Eval 9	
	Day 0	Wks 1-24	Wks 25-32	Wk-2	Wk-4	Wk-8	Wk-12	Wk-16	Wk-20	Wk-24	Wk-32	
	In-person	Remote	Remote	Remote	Remote	In-person or Remote**			Remote	In-person	Remote	
Completed by												
	X											
	X											
Staff + subject	X											
Subject		X										
Subject			х									
Staff				X	X	x	X	x	X	X		
Staff	X			Х	Х	x	X	Х	Х	х	X	
Staff				X	Х	x	X	x	X	Х	X	
Staff + subject				Х	Х	x	Х	Х	Х	х	X	
Staff + subject				X	X	x	X	x	X	X	X	
Investigator + subject						х		х		Х	X	
Staff + subject					Х	x	X	Х	х	х	X	
Staff + subject	X									х		
Staff + subject										х		
Staff + subject											X	
Staff + subject	X **					X **		X **				
	* Data from Eval	11 of the RE	STFUL Study	will be us	ed, since b	oth Evals typic	cally occu	r on the same	day			
	Staff + subject Subject Subject Staff Staff Staff Staff Staff + subject Staff + subject Investigator + subject Staff + subject	In-person	Day 0 Wks 1-24 In-person	Day 0	Day 0 Wks 1-24 Wks 25-32 Wk-2	Day 0	Day 0	Day 0	Day 0	Day 0 Wks 1-24 Wks 25-32 Wk-2 Wk-4 Wk-8 Wk-12 Wk-16 Wk-20 In-person or In-pe	Day 0 Wks 1-24 Wks 25-32 Wk-2 Wk-4 Wks-4 Wks-12 Wk-16 Wk-20 Wk-24	Day 0

		Eval 1	Eval 2	Eval 3	Eval 4	

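### SAP 8.3 shows crude entry-to-Week-24 AE proportions by arm, but any late Arm 2 entrant has under 24 weeks of AE follow-up, so the Arm 2 figure may not be a 24-week risk

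*SAP*

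**What the plan says.** SAP 8.3 sets the main safety display: "The proportion of subjects having one or more adverse events (AEs) between study entry and Week 24 will be presented by Arm". It asks for the same with SAEs, device-related SAEs and device-related AEs, and it reports Arm 1 Weeks 25 to 32 separately. The SAP's Safety Analysis Population is everyone enrolled. Protocol Section 10 has AEs recorded from enrolment to exit.

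Protocol 17.3.2 planned this measure more narrowly, as "The proportion of subjects in Arms 1 and 3 reporting one or more adverse events between study entry and Week 24", pooled over those two arms and limited to treated subjects. Both arms have 24 weeks of device use counted from entry.

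Arm 2 runs on a different clock. For Cohort 2B, protocol 16.2 says: "Subjects will be enrolled either 8-wks, 16-wks, or 24-wks after completion of the RESTFUL Study, +/- 1-wk". Both Arm 2 cohorts finish 24 weeks after RESTFUL completion, give or take a week, and 16.2 draws the consequence itself: "Therefore, the duration of study participation in Arm 2 depends on the delay between RESTFUL Study completion and enrollment in this study". Protocol 16.1 agrees: "Although the duration of Arm 2 states 24-weeks, each subjects participation will vary". Protocol Section 4 adds an intermediate case: "subjects consented 12-wks after The RESTFUL Study will only complete the 16-wk and 24-wk follow-ups". SAP 3.1 keeps the same anchor: "Arm 2 involves assessment during the 24-wks after RESTFUL Study completion".

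One line differs. In protocol 16.12, the description of Arm 2 Evaluation 4, which is also study exit, counts its 24 weeks from the first CT-05 evaluation.

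**The concern.** A subject-level proportion is a 24-week risk only if each subject in the denominator is observed for 24 weeks or until a first event. That suits Arms 1 and 3, for which the protocol planned it. The SAP carries it over to Arm 2, where a late entrant counts fully in the denominator but is observed for a fraction of the time. Arm 2 is labelled the control group, so readers will set the two columns side by side. At equal underlying AE rates they would see more AEs on the device than off it, purely because of unequal follow-up. The distortion runs against the device.

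**Working it through.** The documents give no AE rate, Arm 2 entry mix or sample size, so there is no planned figure to reproduce. Follow-up times come from the documents. Risks, hazard shape and entry mixes are assumptions.

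**Step 1: follow-up.** Entry delay d is in weeks after RESTFUL completion (protocol 16.2, Table 5, and the 12-week example in Section 4). Arm 2 ends at 24 weeks, so follow-up f = 24 − d.

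**Step 2: risk seen over f weeks.** Let p be the true 24-week risk. With a constant hazard, risk over f weeks = 1 − (1 − p)^(f/24).

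| Entry delay d | Follow-up f | p = 20% | p = 40% |
|---|---|---|---|
| 0 | 24 | 20.0% | 40.0% |
| 8 | 16 | 13.8% | 28.9% |
| 12 | 12 | 10.6% | 22.5% |
| 16 | 8 | 7.2% | 15.7% |
| 24 | about 0 | about 0% | about 0% |

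**Step 3: crude Arm 2 proportion.** This is the average of the step 2 risks over the entry mix. For an even 0/8/16/24 mix:

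- p = 20%: (20.0 + 13.8 + 7.2 + 0)/4 = 10.2%
- p = 40%: (40.0 + 28.9 + 15.7 + 0)/4 = 21.1%

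| Assumed entry mix (weeks) | p = 20% | p = 40% |
|---|---|---|
| All at 0 | 20.0% | 40.0% |
| Even over 0/8/16 | 13.7% | 28.2% |
| Half at 0, rest even over 8/16/24 | 13.5% | 27.4% |
| Even over 0/8/16/24 | 10.2% | 21.1% |
| Even over 8/16/24 | 7.0% | 14.8% |

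The 0/8/16 row matters because protocol Table 3 puts Arm 2 entry below 24 weeks, whereas Table 5 allows it at 24.

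**Step 4: does a person-time rate help?** Under a constant hazard λ = −ln(1 − p)/24, expected person-time to first event equals risk divided by λ. Events over person-time therefore return λ whatever the entry mix. At p = 40%, λ = 0.5108/24 = 2.13 per 100 person-weeks in both arms.

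The assumption matters. Suppose half of the cumulative hazard falls in the first 8 weeks after RESTFUL, still with p = 40%. The first-AE rate is then 2.22 per 100 person-weeks in Arm 1 and 1.88 in Arm 2 (even 0/8/16/24 mix), although true risks are equal. Rates reduce the problem but do not remove it.

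**Step 5: scheduled AE checks by Week 24.** Arm 1 has seven (Evaluations 2 to 8). Arm 2 has at most three (Evaluations 2 to 4), and for a late entrant one of these can coincide with enrolment. Ascertainment is unequal as well as follow-up.

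**The case against.** **There may be no late entrants.** SAP 3.4 bases enrolment on the consent rate among subjects who finished RESTFUL once CT-05 was open. Read literally, that leaves Arm 1 and the no-delay Cohort 2A, and the bias is zero. However, SAP 3.1 still offers Arm 2 to earlier completers, as the protocol does. The objection makes the point conditional and does not remove it.

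**The output is descriptive.** A reader might infer that the plan sets up a biased safety test or inflates an error rate. The documents do not support that. SAP 5.1 gives a level for safety tests, but 8.3 names no AE test or between-arm difference, and protocol 17.3.1 makes the endpoint descriptive. Device-related AEs read within Arm 1 are unaffected.

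**The arms differ in other ways.** Arm 2 may change RLS medication, so its true AE rate could differ in either direction. Early removal from Arm 1, which protocol 16.16 allows, would narrow the gap. These points limit how far any size can be trusted, but they do not make unequal follow-up equal.

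**The table shells are not available.** Follow-up time may already appear there, so its absence from the whole plan is not established. The text of 8.3 does not call for it.

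**Two further inferences fail.** The main proportions do not set 32 Arm 1 weeks against 24 in Arm 2, because Weeks 25 to 32 are reported apart. Only the charts of AEs at any time could mix them, if drawn by arm. Nor is the SAP schedule's Day 0 footnote a rival Arm 2 clock, since it only settles which day counts when Evaluation 1 spans several. The protocol 16.12 wording for Evaluation 4 is a real conflict: taken literally, it would give every Arm 2 subject 24 weeks and close the gap.

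**Conclusion.** The point holds conditionally. To the extent that any Arm 2 subject enters late, the crude Arm 2 proportion in SAP 8.3 covers about 16, 12, 8 or 0 weeks for those subjects, against 24 in Arm 1, and understates a 24-week risk. This rests on Arm 2 ending 24 weeks after RESTFUL completion, as protocol 16.2 and SAP 3.1 state.

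The size is illustrative only. Over the mixes shown, a true 20% risk appears as anything from 7% to 20%, and a true 40% risk as anything from 15% to 40%. The top of each range is the no-bias case. What is at stake is how the by-arm safety tables read, not an efficacy conclusion or a test. It is a worthwhile, inexpensive correction.

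**What to change.** In SAP 8.3 and the by-arm AE tables:

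1. Report person-weeks of AE follow-up by arm up to Week 24. Give AE and SAE rates per person-time, both first events and total events per person-week. State that comparing rates assumes a roughly constant hazard.
2. Show Arm 2 AE proportions by entry time (0, 8, 16, 24 weeks), or at least separately for week-0 entrants. Label the pooled Arm 2 proportion as covering unequal follow-up and fewer scheduled AE checks (at most three, against seven in Arm 1).
3. Keep the any-time AE charts that protocol 17.3.2 requires. If they are drawn by arm, mark or separate Arm 1 Weeks 25 to 32.
4. Reconcile the end of Arm 2: the Evaluation 4 description in protocol 16.12 against the completion rule in 16.2, the Arm 2 schedule footnote and SAP 3.1.

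A delayed-entry cumulative incidence on time since RESTFUL is optional. If AE-proneness varies between subjects it can err the other way: a simulation with an assumed gamma frailty of variance 1 and an even 0/8/16/24 mix gave 43% in Arm 2 against 40% in Arm 1 at equal hazards. Its early weeks would also rest only on Cohort 2A, who declined Arm 1.

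The cost is a little table and text work, since the enrolment, AE onset, exit and RESTFUL completion dates are already needed to run Arm 2. The drawback is imprecise Arm 2 rates, because late entrants contribute little time.
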